A. Baseline (Pretreatment) assessment- A full physical examination will be performed and 545 546 vital signs (blood pressure, respiration and temperature) determined. Trained personnel using 547 standardized protocols at the baseline and follow-up examination will obtain anthropometric 548 measurements and blood specimens. Absolute body weight, height, waist and hip 549 circumference, body fat distribution (waist/hip {WHR}) and waist/height ratio ({WHtR}) and blood pressure (BP) will be determined. Body weight will be measured to the nearest 0.1 kg 550 551 using a calibrated digital scale with participants in light clothing and no shoes. Height will be 552 measured to the nearest centimeter. The total body adiposity (total fatness), defined as the accumulation of body fat without regard to regional distribution, will be expressed as BMI and 553 calculated as weight $(kg)/(height (m))^2$. The circumference measurements will be taken in the 554 upright position using a 15-mm width flexible metric tape held close to the body but not tight 555 enough to indent the skin. Waist circumference (WC) will be measured at the narrowest level 556 557 midway between the lowest ribs and the iliac crest and hip circumference measured at the 558 widest level over the buttocks while the subjects are standing and breathing normally. The WHR 559 and WHtR will be calculated for measure of body fat distribution.

Oral glucose tolerance tests (OGTTs) with glucose (G) and insulin (I) measured at 0, 30, 60, 560 561 and 120 after glucose load to assess diabetes, fasting (FBG) and mean blood glucose (MBG) concentrations, insulin resistance and pancreatic beta-cell function will be determined prior to 562 randomization and at 30-32 weeks after full doses of study medications are reached. Mean 563 564 blood glucose (MBG) concentrations will be calculated by summing glucose values obtained at 0,30,60 and 120 minutes during the OGTT and dividing by 4. At the initial lab evaluation, a 565 566 complete metabolic profile (Chem 12) and calculated eGFR, TSH, prolactin, hemoglobin A1C, and 567 beta-hCG levels will be determined for study inclusion. A baseline blood sample will also be 568 used to measure an androgen profile (total testosterone [T], dehydroepiandrosterone sulfate 569 [DHEAS], sex hormone-binding globulin [SHBG]), and a lipid panel (total cholesterol, high-density 570 lipoprotein [HDL-C], low-density lipoprotein [LDL-C], and triglycerides [TRG].

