 - dates and initials of person responsible for Investigational Product dispensing/ accountability.

Destruction of Investigational Product- If the study drugs are to be destroyed on site, it is the investigator's responsibility to ensure that arrangements have been made for disposal, and that procedures for proper disposal have been established according to applicable regulations, guidelines, and institutional procedures. Appropriate records of the disposal will be maintained.

680

681 **Biological Sampling Procedures**

682 Laboratory Measures

683 Hormonal and metabolic parameters will be measured at baseline and 30 weeks of 684 treatment. All participants will undergo a standard 2-h oral glucose tolerance test (OGTT) after an overnight fast (10–12 h). Blood samples for the determination of glucose and insulin levels 685 686 will be obtained in the fasting state (time 0) and collected at 1/2, 1, and 2 h after a standardized 687 75 g oral glucose load (OGTT with INS). Blood samples will be centrifuged, divided into aliquots, 688 and assayed. Plasma glucose levels will be determined with a glucose analyzer using the glucose 689 oxidase method (Glucose Reagent Kit, Bayer Newbury, UK). Serum insulin will be determined in 690 all samples in duplicate by microparticle enzyme immunoassay (Abbott AxSYM System, Abbott 691 Laboratories, Abbott Park, IL). Levels of total cholesterol, high-density lipoprotein cholesterol 692 (HDL-C) and triglycerides will be determined in the initial basal sample using standard enzymatic 693 colorimetric assays on an automated clinical chemistry analyzer whereas low-density lipoprotein cholesterol (LDL-C) will be calculated according to the Friedewald equation. Electrolytes, serum
creatinine, and liver enzymes will be measured using standard automated kinetic enzymatic
assay. Circulating levels of TSH, prolactin, ß human chorionic gonadotropin (ßhCG), testosterone,
sex-hormone binding globulin (SHBG) and DHEAS will be measured using a two-site sandwich
immunoassay with direct chemiluminometric technology (Diagnostic Products, Los Angeles, CA).
The intra- and interassay coefficients of variation are less than 7 and 11%, respectively, over the
sample concentration range.

701 Assessment of Insulin Sensitivity and Secretion

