702 Indices of insulin sensitivity and secretion using the serum glucose and insulin 703 concentrations obtained in the fasting state and during the 2hr OGTT will be computed by 704 several previously validated measures. Fasting and glucose-stimulated insulin sensitivity will be 705 estimated by homeostasis model assessment of insulin sensitivity (HOMA-IR) and by Matsuda's 706 insulin sensitivity index (SI_{OGTT}). Early pancreatic beta (β)-cell response will be estimated as the 707 insulinogenic index (IGI) derived from the ratio of the increment of insulin to that of glucose 30 708 minutes after a glucose load (insulin 30 min – insulin 0 min/glucose 30 min – glucose 0 min) 709 corrected for by the relative level of insulin resistance (IGI/HOMA-IR). The area under the curve (AUC) for glucose and insulin will be calculated using the mathematical model developed by Tai 710 711 using measures obtained during the OGTT. An estimation of β -cell compensatory function, the 712 insulin secretion-sensitivity index (IS-SI) will be derived by applying the concept of the 713 disposition index to measurements obtained during the 2-h OGTT. The composite IS-SI is 714 defined as the product of 1) insulin secretion as measured by insulinogenic index (IGI) and 2) insulin sensitivity as measured by the Matsuda index ($\Delta INS/\Delta GLU$ 30 x Matsuda SI_{OGTT}). The IS-SI 715 716 is a validated OGTT-derived measure of β -cell function analogous to the disposition index 717 obtained from the intravenous glucose tolerance test. Improving β -cell compensatory function 718 (increasing insulin sensitivity and enhancing insulin release after an oral glucose load) is 719 reflective of improvement and/or delays in declining glucose tolerance.

The most frequent biochemical parameters of androgen excess include elevated total testosterone or free androgen index (FAI). Baseline blood samples will be collected for measurement of total testosterone (T) and sex hormone-binding globulin (SHBG) concentrations. The free androgen index (FAI) is calculated from the total T concentration (nmol/l)/ concentration of SHBG (nM/L) x100. While clinical markers of hyperandrogenism in females include cutaneous manifestations such as the presence of acne, hirsutism and/or male pattern alopecia, many of these will not be altered with 30 weeks of therapy.

727

728 Collateral Research

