For all analyses, in which the measures are continuous, data from evaluable subjects will be submitted to a repeated-measures general linear model (SS/ Drug treatments x repeated measures ANOVA) including the arm of drug treatment (liraglutide 3mg vs. placebo) as the between-subjects effect, and the visit (baseline and 30 wks) as the within-subjects effect. To evaluate the differences in the response to each treatment over visits, the interaction effect will be calculated. Baseline comparisons between groups will be made by one-way ANOVAs.

Frequency of patients achieving a body weight reduction of at least 5% and 10% before and after treatment will be compared with the McNemar test (complex chi square $[\chi^2]$ for paired data), which formally tests for a change between the observed proportions of k related samples. Dysglycemia occurrence before and after different treatment will also be compared with the McNemar test. The difference in frequency of menstruation before and aftertreatment will also be compared using the McNemar test.

Data will be analyzed on completed treatment parameters where relevant (evaluable population). The evaluable population is defined as all randomized subjects who complete treatment through week 30-32 week. Results will be reported as mean +/- S.E.M for normally distributed data and as median (interquartile range) if the distribution is not normal. Categorical data will be presented as percentage. P < 0.05 is considered statistically significant.

773

774 Sample Size and Justification

775 A priori sample size analysis was performed using the online calculator provided by the 776 Hospital Mallinckrodt General Clinical Massachusetts General Research Center (http://hedwig.mgh.harvard.edu/sample size/size.html). To calculate sample size, we used the 777 778 standard formula suggested for clinical trials by considering a type one error (α) of 0.05 and type 779 two error (β) of 0.20 (power = 80%). Sample size calculation revealed that 57 participants 780 randomized in a 2:1 ratio (liraglutide: placebo) were needed. Using a 30% drop-out rate, the 781 study is designed to recruit 92 patients, enroll 48 liraglutide and 24 placebo to ensure that the 782 number of subjects completing the study (38 LIRA/19 PL) as derived by the sample size 783 calculation is met.

784

785 Ethical and Regulatory Requirements

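### FAI and the other endpoints analysed as continuous are tested by a change-score comparison that leaves the collected baseline unused as a covariate; this affects precision only, by an unknown amount

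*Combined protocol and SAP*

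**What the plan says.** All references are to the combined protocol and SAP.

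- **Model.** Statistical Methods sends continuous measures from evaluable women to a repeated-measures general linear model with treatment arm between subjects "and the visit (baseline and 30 wks) as the within-subjects effect".
- **Treatment test.** "To evaluate the differences in the response to each treatment over visits, the interaction effect will be calculated". No covariate is named for any analysis.
- **Other use of baseline.** "Baseline comparisons between groups will be made by one-way ANOVAs". No consequence is attached to the result.
- **Endpoints covered.** FAI is co-primary 2 (Primary endpoints) and falls under this rule, as do the secondary metabolic, anthropometric, lipid and blood-pressure measures. Menstruation frequency does not: the same section assigns it to the McNemar test.
- **Baseline is collected.** The baseline assessment covers "Absolute body weight, height, waist and hip" circumference, and the baseline sample is "used to measure an androgen profile (total testosterone [T], dehydroepiandrosterone sulfate" sulfate and SHBG. Laboratory Measures adds: "Hormonal and metabolic parameters will be measured at baseline and 30 weeks of" treatment.
- **Size.** Sample Size and Justification plans for the "number of subjects completing the study (38 LIRA/19 PL) as derived by the sample size" calculation.

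**The concern.** A change score assumes that a woman who starts one unit higher finishes one unit higher within her arm. ANCOVA estimates that slope. If the true slope is well away from 1, the change score leaves baseline-related noise in the arm comparison that could have been removed. FAI is a ratio of two assayed quantities, measured once at each end, and Laboratory Measures gives an interassay coefficient of variation of up to 11%. A slope other than 1 is therefore plausible, although the documents give none. With 19 planned placebo completers, precision lost on a co-primary endpoint could matter.

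**Working it through.** **Inputs from the plan.** Alpha 0.05, power 80%, 57 completers split 38/19 (Sample Size and Justification).

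**Assumptions, not in the documents.** Two-sided testing; ρ, the baseline/week-30 correlation; k, the baseline SD divided by the week-30 SD.

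**1. The plan's own figure.** The 57 cannot be reproduced, because no endpoint, effect size or SD is given. Back-solving for 38/19:

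d = (1.960 + 0.842) × √(1/38 + 1/19) = 2.802 × 0.281 = 0.787 (normal), or 0.8013 by noncentral t on 55 df.

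The value 0.8013 serves below as the effect that gives the change-score test 80% power. It is an anchor, not evidence that FAI was powered at 80%.

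**2. The planned test is the change-score test.** With two visits, the interaction contrast is the difference between arms in mean (week 30 minus baseline). On simulated 38/19 data, interaction F = 3.3891 and the squared t on change = 3.3891, both with p = 0.0710.

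**3. Variance ratio, common slope.** Set the week-30 SD to 1. The within-arm variance of change is 1 + k² − 2ρk. The ANCOVA residual variance is 1 − ρ². So

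R = (1 − ρ²) / (1 + k² − 2ρk).

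The denominator exceeds the numerator by (k − ρ)², so R equals 1 only when ρ = k, that is, when the slope ρ/k is 1. Example: k = 1, ρ = 0.5 gives R = 0.75/1.00 = 0.75 and d/√R = 0.8013/0.866 = 0.925, hence 90% power on 54 df.

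**4. Power at 38/19 when the change score has 80%.** The second power column multiplies R by (1 + 1/53) to charge for estimating the slope. The last column is a simulation of ANCOVA with an HC3 standard error (normal data, common slope, 100,000 trials per row, 54 df).

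| k | ρ | slope ρ/k | R | ANCOVA | slope charged | HC3 |
|---|---|---|---|---|---|---|
| 1 | 0.5 | 0.50 | 0.750 | 89.9% | 89.3% | 87.8% |
| 1 | 0.7 | 0.70 | 0.850 | 85.9% | 85.3% | 83.6% |
| 1 | 0.9 | 0.90 | 0.950 | 82.0% | 81.2% | 79.5% |
| 0.7 | 0.5 | 0.71 | 0.949 | 82.0% | 81.3% | 79.3% |
| 0.7 | 0.7 | 1.00 | 1.000 | 80.0% | 79.2% | 77.4% |
| 0.7 | 0.9 | 1.29 | 0.826 | 86.9% | 86.3% | 84.7% |
| 1.25 | 0.5 | 0.40 | 0.571 | 96.0% | 95.6% | 94.7% |
| 1.25 | 0.7 | 0.56 | 0.628 | 94.2% | 93.8% | 92.8% |
| 1.25 | 0.9 | 0.72 | 0.608 | 94.9% | 94.5% | 93.5% |

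Entry on elevated testosterone and/or FAI (Subjects) may narrow the baseline spread, so k below 1 is possible.

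**5. False positives, common slope.** Simulated at k = 1 and ρ = 0.5, 0.7, 0.8, the rates were 4.7%, 5.2%, 4.3% for the change score and 4.8%, 5.0%, 4.2% for ANCOVA. Both hold the level.

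**6. Unequal slopes under 2:1.** Ten assumed cases were simulated, with slopes from 0.4 to 1.1 and residual SD 0.3 to 0.6 on a baseline SD of 1.

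- The variance ratio of single-slope ANCOVA to change score runs from 0.75 to 1.18.
- With a centred baseline-by-arm term it runs from 0.65 to 1.02.
- False-positive rates are 2.0-9.1% for the planned test, 5.3-7.5% for ANCOVA with the usual standard error, and 4.2-4.8% for ANCOVA with HC3.

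**7. Percent change in weight (1a).** Assume mean weight 110 kg, SD 15-25 kg, SD of percent change 6 points and a difference of 4.8 points. Power is then about 80% for percent change alone and about 79% with baseline weight as covariate. There is no gain.

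**The case against.** The strongest case against acting is that this is a choice between two legitimate analyses. Each woman's baseline is already used, by subtraction. Neither ρ nor k is in the documents, and nothing ties the 80% anchor to FAI. The gain vanishes within the assumed grid when the slope is near 1.

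ANCOVA also carries a risk. In the eight unequal-slope cases where the liraglutide slope is below the placebo slope, the planned test is conservative (2.4-4.1% in one rerun), while single-slope ANCOVA with the usual standard error is mildly anti-conservative (5.2-7.5%). Only in the two reverse cases is the planned test the worse one (9.2-9.7% against 6.9-7.5%).

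Most of this stands. It confines the point to precision and rules out a claim of known size. The last argument changes the remedy without defeating it: HC3 held 4.2-4.8% in the same ten cases, at the power cost shown above.

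A reader might infer that the planned FAI comparison is biased or invalid. The documents do not support that. Randomization makes the change-score estimate unbiased, and its level holds under a common slope. A reader might also infer that every continuous endpoint is affected. Menstruation frequency is not, since it goes to McNemar.

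**Conclusion.** The point holds as a worthwhile, inexpensive improvement to precision for FAI and the secondary endpoints analysed as continuous. The equivalence with a change-score t-test is exact, and no baseline covariate is named.

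The size of the gain is not known from the documents. Under a common slope and equal SDs, 80% would become about 89-90%, 85-86% or 81-82% at assumed correlations of 0.5, 0.7 and 0.9. With k = 0.7 and ρ = 0.7 there is no gain (79-80%). With HC3 the equal-SD figures fall to about 88%, 84% and 80%, so the benefit is material only if the true slope is well away from 1.

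It would go too far to conclude that the trial is underpowered for FAI, or that it forfeits a stated number of points. The plan gives no effect size, SD or correlation from which to show either. No gain is claimed for co-primary 1a.

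**What to change.** In Statistical Methods, for FAI and the secondary endpoints analysed as continuous:

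- Replace the two-visit interaction test with ANCOVA of the week-30 value on arm, with the baseline value of the same variable as covariate. Using change as the outcome gives the same adjusted arm difference.
- Keep the plan's transformation rule, apply it to both visits, and report a ratio if logs are used.
- Specify a heteroscedasticity-robust standard error such as HC3. Confirm that the named software (SPSS 15.1) can produce it, or name another program.
- Optionally add a centred baseline-by-arm term as a pre-specified supportive analysis. Its standard error must allow for the estimated centring mean. In the ten cases the usual one gave 5.8-12.0% false positives, and the corrected one 4.7-5.0%.

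**Cost.** No new data are needed. If the true slope is 1, estimating it costs under 1 point of power with the usual standard error (80.0% to 79.2%), and nearly 3 points in all with HC3 (to 77.4%). If slopes differ markedly between arms under 2:1, some precision can be lost (variance ratio up to about 1.2 in the assumed cases); the centred term largely removes that loss.

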The primary objectives of this study are to compare the therapeutic impact of liraglutide 368 3 mg versus placebo on reduction of body weight and biochemical hyperandrogenism (as 369 determined by the free androgen index) in obese non-diabetic women with PCOS. We will 1) 370 determine the percentage of participants achieving \geq 5% reduction in baseline body weight with 371 each treatment and 2) assess the inhibition of biochemical hyperandrogenism (ovarian androgen 372 production and sex hormone binding capacity) in response to each treatment.

373 Secondary study objectives

The secondary study objectives are to determine the effect of treatment with antiobesity medication versus placebo on anthropometric, **clinical**, hormonal and metabolic parameters in non-diabetic obese women with hyperandrogenism.

377

378 EFFICACY VARIABLES/MEASURES

379 *Primary endpoints*

The co-primary end points are to compare obese women with PCOS receiving liraglutide 3mg (LIRA 3 mg) with those receiving placebo on body weight and bioavailable ovarian androgen

- 382 concentrations as determined by:
- 1a. percent change in body weight from baseline to week 30 and
- 1b percentage of participants achieving ≥5% reduction in body weight from baseline
 to week 30
- 3862reduction of free androgen index [FAI=testosterone (T)/sex hormone binding387globulin (SHBG) levels] from baseline to 30 weeks
- 388 Secondary endpoints
- 389 We will further examine the impact of the administration of these pharmacotherapies in obese
- 390 non-diabetic PCOS women on:
- 391 Anthropometric and Clinical Indices
- Change from baseline of body mass index [BMI], absolute body weight, waist circumference (WC), waist: hip ratio (WHR), waist-height ratio (WHtR), and whole-body dual-energy X-ray absorptiometry [DXA]) measures of body composition (trunk fat mass and truck fat/extremities fat ratio) to determine the relative contribution of changes in fat mass (FM) vs. lean mass (LM) to overall weight loss at week 30
- 2. Compare women with hyperandrogenism for frequency of patients achieving a body
 weight reduction of at least 10% [Time Frame from baseline to 30 weeks]
- 399 3. Change in menstruation frequency (normalized to the number of menstruations per year) from before and after 30 weeks of treatment
- 401 Metabolic Parameters
- 402 1. Change in glycemic values from baseline to 30weeks
- 403 2. Fasting and 2 hour glucose levels after an OGTT

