- 618 Patients on LIRA -**S**tart injection 0.6 mg SC QD 1week, step up to 1.2 mg SC QD 1 week, to 619 1.8 mg SC QD 1 week, 2.4 mg SC QD 1week, to a max dose of 3.0 mg SQ daily.
- Patients on PL -Start injection 0.6 mg SC QD 1week, step up to 1.2 mg SC QD 1 week, to
 1.8 mg SC QD 1 week, 2.4 mg SC QD 1week, to a max dose of 3.0 mg SQ daily.

All patients will be called monthly to document the results of their home pregnancy tests and to assess compliance with the medication. Patients will receive the same counseling concerning the benefits of lifestyle modification through diet and exercise. The patients will be also encouraged to increase daily exercise (such as walking, using stairs) although this will not be formally assessed. The participants will receive further encouragement to adhere to the regime by frequent contact using follow-up phone calls. Side effects of the treatment and reason for any withdrawals from the study will be recorded.

629 C. *Week 16-18 assessment-* Patients will return to clinic for an 18-week re-evaluation of 630 clinical and anthropometric variables (height, weight, body mass index [BMI], waist and hip 631 circumference and blood pressure) and a safety assessment. A serum pregnancy test and 632 complete metabolic profile (Chem 12) and calculated eGFR will also be performed. Side effects 633 of the treatment and reason for any withdraws from the study will be recorded. Another 18 634 weeks of medication will be dispensed and 4 home pregnancy test kits following a negative 635 serum pregnancy test.

D. *Final (week 30-32) assessment-* After 28 weeks of treatment, patients will be scheduled for final evaluation. They will be instructed to stop medications 1 week prior to their laboratory assessment visit. All laboratory tests (except prolactin, TSH and hemoglobin A1C) will be repeated. All anthropometric parameters and physical including vital signs and DXA will again be performed and calculations will be repeated for post-treatment effects.

641

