1021 Any significant worsening noted during interim or final physical examinations, 1022 electrocardiogram, x-ray filming, any other potential safety assessment required or not required 1023 by protocol should also be recorded as a nonserious or serious AE, as appropriate.

- 1024
- 1025 Discontinuations

1026 The reason for a subject discontinuing from the study will be recorded in the patient chart. 1027 A discontinuation occurs when an enrolled subject ceases participation in the study, regardless 1028 of the circumstances, prior to completion of the protocol. The investigator must determine the 1029 primary reason for discontinuation. Withdrawal due to adverse event will be distinguished from 1030 withdrawal due to insufficient response according to the definition of adverse event noted 1031 earlier. The final evaluation required by the protocol will be performed at the time of study discontinuation. The investigator will record the reason for study discontinuation, provide or 1032 1033 arrange for appropriate follow-up (if required) for such subjects, and document the course of the subject's condition. They will also to be reported to Woman's Hospital Foundation 1034 1035 Institutional Review Board at [contact] and Woman's Health Research Department at 1036 [contact].

1037

1038

Subjects MUST discontinue investigational product for any of the following reasons:

- Withdrawal of informed consent (subject's decision to withdraw for any reason).
- Any clinical adverse event, laboratory abnormality, or intercurrent illness, which, in
 the opinion of the investigator, indicates that continued participation in the study is
 not in the best interest of the subject.
- 1042 Pregnancy
- 1043oInstruct subjects to contact the investigator or study staff immediately if they1044suspect they might be pregnant (e.g., missed or late menstrual period) at any1045time during study participation. Institutional policy and local regulations should1046determine the frequency of study pregnancy tests for subjects enrolled in the1047study.
- 1048oThe investigator must immediately notify Novo Nordisk if a study subject1049becomes pregnant.
- Loss of ability to freely provide consent through imprisonment or involuntary incarceration for treatment of either a psychiatric or physical (e.g., infectious disease) illness.

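### Continuous endpoints are modelled at two visits in completers only, so the week 16-18 weights, and every woman who leaves after them, drop out of the co-primary weight comparison

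*Combined protocol and SAP*

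**What the plan says.** Statistical Methods sets one model for all continuous outcomes: "For all analyses, in which the measures are continuous, data from evaluable subjects will be submitted to a repeated-measures general linear model". The between-subjects factor is treatment arm. The within-subjects factor has two levels: "and the visit (baseline and 30 wks) as the within-subjects effect". The analysis set is restricted to completers: "The evaluable population is defined as all randomized subjects who complete treatment through week 30-32 week".

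The schedule collects more than this. Study Assessments, part C (week 16-18), re-measures "clinical and anthropometric variables (height, weight, body mass index [BMI], waist and hip" "circumference and blood pressure) and a safety assessment". The efficacy-type measurements are thus listed separately from the safety assessment. The Discontinuations section adds: "The final evaluation required by the protocol will be performed at the time of study discontinuation".

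The first co-primary endpoint is "percent change in body weight from baseline to week 30". BMI, waist and blood pressure are secondary endpoints over the same interval. No section gives the week 16-18 or discontinuation values a role in a model, an imputation or a sensitivity analysis.

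**The concern.** In a 72-woman trial that allows for 30% drop-out, the plan discards a mid-trial measurement of a co-primary outcome that is likely to be well correlated with the week-30 value. Two things are at stake.

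- **Precision.** Women seen at week 16-18 who then leave carry information about week 30, and the plan does not use it.
- **Bias.** If leaving depends on how much weight a woman has lost by week 18, a comparison of completers is distorted. A model that conditions on the week 16-18 value can correct for the part of that dependence it captures. The Discontinuations section recognises insufficient response as a reason for withdrawal, but gives no expected frequency.

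**Working it through.** **1. Visits measured and visits used.** Weight, BMI, waist, hip and blood pressure are measured at baseline, week 16-18 and the final visit, and at discontinuation where that applies. The model uses baseline and week 30. FAI, OGTT, lipids and DXA are measured at baseline and the final visit only, so for them nothing is left out.

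**2. Does adding the visit help on its own?** One complete data set was simulated with 38 and 19 women. The two-visit test of change and a three-visit model with unstructured covariance and saturated means gave the same week-30 contrast (-0.711) and the same t (-3.66). When everyone analysed has a week-30 value, the middle visit adds nothing to the week-30 contrast. The gain appears only when women without week 30 are kept.

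**3. Inputs for the size.**
- From Sample Size and Justification: 48 and 24 women enrolled; 30% drop-out. This gives 0.70 x 72 = 50.4 women at week 30 (33.6 and 16.8). The plan's own target of 57 completers corresponds to a smaller loss, (72 - 57)/72 = 20.8%, so both rates are shown.
- The 57 itself cannot be reproduced, because no effect size, SD or response rate is given.
- Assumed, because the documents give no figures: SD of percent weight change 4 at week 18 and 5.5 at week 30; correlation ρ between the two changes of 0.7 to 0.9; true week-30 difference of -4.5 points; 40% or 70% of drop-outs leaving after the week 16-18 visit.

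**4. Precision under random drop-out.** Per arm, with m women seen at week 30 and n seen at week 16-18, the variance of the week-30 mean is approximately s²[ρ²/n + (1 - ρ²)/m]. Relative to completers only, the ratio is R = ρ²(m/n) + 1 - ρ², and the standard error falls by 1 - √R.

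Worked case (30% drop-out, 40% of it after week 18, ρ = 0.85):
- m/n = 0.70/(0.70 + 0.4 x 0.30) = 0.70/0.82 = 0.854, or about 59 women seen at week 16-18 against 50 at week 30
- R = 0.7225 x 0.854 + 0.2775 = 0.894, so 1 - √0.894 = 5.4%
- completers-only SE = 5.5 x √(1/33.6 + 1/16.8) = 1.64; with week 16-18, 1.64 x 0.946 = 1.55

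Simulation of 4,000 trials in this setting gave 1.655 and 1.565, also a 5.4% reduction.

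| Drop-out | Share after week 18 | m/n | SE reduction, ρ = 0.7 | SE reduction, ρ = 0.9 |
|---|---|---|---|---|
| 30% | 40% | 0.854 | 3.7% | 6.1% |
| 30% | 70% | 0.769 | 5.8% | 9.8% |
| 20.8% | 40% | 0.905 | 2.4% | 3.9% |
| 20.8% | 70% | 0.844 | 3.9% | 6.5% |

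Simulation at 30% drop-out gave 4-7% (40% after week 18) and 5-11% (70% after week 18).

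**5. Bias under response-dependent drop-out.** Let the log-odds of leaving after week 18 rise by 1 per SD of poorer week-18 loss (odds ratio about 2.7). The completers-only two-visit estimate then averaged -4.00 to -4.16 against a true -4.5, a shrinkage of 0.34 to 0.50 points. The analysis using week 16-18 returned -4.46 to -4.51.

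**The case against.** **The plan is internally consistent.** The endpoints are changes to week 30, and a two-visit model matches that target. This stands: the point is unused data, not a contradiction or an invalid test.

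**The gain comes from the population.** A reader might infer that the two-level visit factor is a fault in its own right, separate from the completers-only restriction. Step 2 shows otherwise, since within completers the week-30 contrast does not move. The reverse also matters: admitting all randomised women while keeping two visits would still leave a woman last weighed at week 18 without a place in the model. The two changes belong together, and if the completers-only population is criticised elsewhere, the gain should not be counted twice.

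**Leavers should have a later weight.** The Discontinuations section requires a final evaluation on leaving, so many women who go between weeks 18 and 30 should have a weight later than week 16-18. This stands. The simulation does not model that weight, and the plan gives it no analytic use either, so the fix must assign it a place.

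**Is week 16-18 the only on-drug reading?** A reader might infer this from part D of Study Assessments, which says of the women "They will be instructed to stop medications 1 week prior to their laboratory assessment visit". It is likely for scheduled readings but not established. The stop is tied to the laboratory visit, and the text does not say that weight, waist and blood pressure are taken at that same visit. Discontinuation evaluations may also fall on or close to drug.

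**Do the values go wholly unused?** A reader might infer that too. Vital signs feed the safety review, so week 16-18 blood pressure has that use. What is missing is a specified efficacy analysis.

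**The size is assumed.** The SDs, correlation, effect and odds ratio have no source in the documents. If good responders left more often, the bias would change sign.

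**Conclusion.** The point holds in this form: the two-level visit factor and the completers-only set together exclude the week 16-18 and discontinuation measurements from every specified efficacy analysis, including that of co-primary weight change.

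At the plan's 30% drop-out, with correlations of 0.7 to 0.9, the loss is about 4-11% in the standard error of the week-30 difference. At the 20.8% implied by 72 enrolled and 57 completing, it is smaller, about 2-7% by the formula. If poor responders leave more often, at the assumed strength, about 0.3-0.5 points of bias on a 4.5-point effect would be avoided. The precision gain alone is modest, and protection against selective drop-out is the better reason to act.

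Nothing is gained for FAI, OGTT, lipid or DXA measures. The responder endpoint (at least 5% weight loss) is not addressed by this change.

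**What to change.** In Statistical Methods, for percent weight change, BMI, waist, WHR, WHtR and blood pressure, replace both the evaluable-subjects restriction and the two-level visit factor, as follows:

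- **Population:** all randomised women with at least one post-baseline value.
- **Model:** a mixed model for repeated measures with change at week 16-18 and at week 30 as the response, arm-by-visit and baseline-by-visit terms, and an unstructured covariance.
- **Discontinuation values:** assigned to the nearest scheduled visit by a window stated in advance.
- **Tested result:** the week-30 arm contrast. The week 16-18 contrast is reported as supportive.

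FAI, OGTT, lipid and DXA measures keep two visits.

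The cost is SAP wording and a different analysis procedure, with no new visits, measurements or patients. The small downside is that the model assumes drop-out depends only on observed values. The SAP should state that assumption.
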